The study will be designed as a multicentre, prospective, randomised, open, blinded endpoint clinical trial. Consecutive bedridden patients (a score of 3 or 4 per item 6 of the NIHSS or the impossibility to maintain an upright position such as in the case of ataxia in patients with hemorrhagic cerebellar stroke) 18 years of age or older with primary intracerebral hemorrhage on CT scan or patients with intracranial hemorrhage during treatment with oral anticoagulants (after reversal), will be assessed for eligibility.

Exclusion criteria will include: intracranial hemorrhage due to vascular malformation, bleeding disorders (defined by a prothrombin time more than 30% longer than the control value or a platelet count of less than 100,000 per cubic millimetre), renal failure defined as a clearance of creatinine less than 30, severe hepatic failure, known neoplastic disease, pregnancy, necessity of therapeutic anticoagulant or antiplatelet agents for concomitant disease, participation in

other ongoing clinical trials or patient refusal to consent. The study protocol will be approved by the local ethics committees of the participating hospitals.

Study design and interventions

Patients will be randomized 72 h after the onset of symptoms after having undergone a brain CT scan which will be considered the baseline examination. This CT must exclude a re-bleeding compared to the CT at admission. In the face of re-bleeding, patients will be excluded from randomization. Re-bleeding will be defined as an increase of 10% in the basal volume measured by standardized and validated criteria (9).

Patients will be randomized over the phone using a random list of numbers (even numbers – treatment A; odd numbers – treatment B) to receive enoxaparin 0.4 ml die plus standard therapy (group A) or standard therapy alone (group B). Treatment with enoxaparin is scheduled to last 10 ± 2 days. A venous eco-Color-Doppler examination with a compression test will be performed bilaterally on the lower limbs 10 ± 2 days following the start of treatment. This exam will evaluate the following three points: the common femoral vein at the groin, superficial femoral vein at the mid-thigh and the popliteal vein at the popliteal fossa up until the trifurcation.

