Included patients will be visited on a daily basis during their hospital stay in order to monitor any complications as well as check for symptoms and signs of venous thromboembolism. An ultrasound exam of the lower limbs will be performed expediently on any patient having clinical signs of suspected deep venous thrombosis. If this exam results being negative, the patient will undergo a second ultrasound exam according to the timetable set out in the protocol. An

ultrasound exam of the lower limbs and a CT thoracic angiography will be performed expediently on any patient having clinical signs of pulmonary embolism. If these exams result being negative, the patient will undergo a second ultrasound exam according to the timetable set out in the protocol.

A positive result from either the CT thoracic angiography or an ultrasound exam will necessitate a treatment with heparin (unfractionated or at a low molecular weight), warfarin or vena cava filter according to clinical need. Brain CT scan will be performed 10 ± 2 days from the start of treatment or whenever there is a worsening of the clinical condition, defined as an increase of 4 points or more on the NIHSS score. Treatment with heparin will be suspended whenever CT shows an increase of at least 10% in the volume of cerebral hemorrhage, notwithstanding clinical condition. Lesion volume will be measured with the methodology elaborated by Broderick et al. (9). Antithrombotic treatment different from that which is planned by the protocol during the treatment period will be forbidden except in the case of clinical need (i.e. diagnosis of venous thromboembolism). Follow-ups at 30 and 90 days after cerebral hemorrhage will be performed either in-clinic or over the phone in order to monitor for any clinical signs of venous thromboembolism or re-bleeding. All deaths will be recorded.

The final follow-up, at 90 days, will be carried out over the phone by an independent physician blinded to the treatment received. After the treatment period outlined in the protocol (10 ± 2 days), the treating physician will be able to determine future therapy.

In the event of positive ecographs, patients can be treated with heparin (unfractionated or low molecular weight heparin), warfarin or vena cava filter, according to necessity.

Neuroradiological exams as well as pulmonary angio-CTs will be evaluated by the study coordinating centre (University of Perugia) blinded to the clinical condition of the patients.

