Venous thrombo-embolic and intra- and extra-cranial hemorrhagic events will be judged blindly on the type of treatment received by the following physicians from the University of Perugia: [name], [name], [name], [name], [name] e [name].

The study will be divided into 3 sections: I. Patients 1-120; II. Patients 121-240; III. Patients 241-406.

Given the complexity of the study, a data safety monitoring board (DSMB) will be responsible for evaluating the progress of the study after the closure of section I. The second evaluation will be performed by the DSMB after the closure of section II. The DSMB will be composed of three independent and external physicians, one of which is a statistician, to the coordinating centre: [name], University of Bologna, [name], University of Perugia and [name], University of Ancona.

Risks of treatments and procedures.

Risks include intra and extracranial hemorrhagic complications associated with heparin use and/or complications such as ulcers and subcutaneous hematomas due to the use of elastic stockings. There are no anticipated risks due to diagnostic procedures, given that all of the exams outlined in the protocol will be usually performed in clinical practice.

Risk-benefit evaluation

Patients with ICH have a reported risk of ~ 20% for thromboembolic complications. The use of prophylactic heparin, where it has been tested on cancer, orthopedic and neurosurgery patients, has reduced the incidences of these events and their respective mortality rates and hospital stays. These studies have also reported an increase in ICH in patients treated with heparin compared to placebo. Whereas, at the end of follow-up, a net benefit, which was statistically significant, remained for those patients treated with heparin compared to those on placebo.

End-points

The primary endpoint of this study will be made up of either: 1) symptomatic venous thromboembolism objectively documented as proximal/distal DVT or pulmonary embolism or 2) asymptomatic proximal/distal DVT documented by ultrasound at the end of follow-up. Diagnostic criteria which has already been validated will be utilized (10).

Secondary end-points:

1. The number of symptomatic and asymptomatic intracranial bleedings as described above in Methods;

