2. The number of extracranial bleedings will be divided into two groups: major and minor. Major bleedings will be defined as 1) presence in critical organ sites including the retroperitoneal and intraocular spaces, 2) a reduction of 2 or more gr/dL of hemoglobin or the need to carry out a transfusion of 2 or more units of concentrate red blood cells or 3) fatal bleeding. Medical

intervention, including any interruption of study treatment, will be considered clinically relevant but not a major bleeding for all the events that do not satisfy the above described criteria. All other bleedings will be considered minor;

3. The combined end-point of disability (modified Rankin Scale ≥ 3) and mortality for any cause at 90 days;
4. Mortality alone at 90 days.

For each endpoint event, centres will be required to submit adequate documentation which will be evaluated by the Adjudication Committee.

Statistical analysis

The primary and secondary endpoints will be evaluated with an intention to treat analysis that will include all the randomized patients in both groups which will be treated or not, depending on the randomized group. Differences between the two groups will be calculated using the Chi-square test. The odds ratio, as well as relative risk will be calculated with confidence intervals. All predefined endpoints will be assessed without adjusting for confounding factors. Post-hoc analysis (logistic regression) will be carried out, in the face off any possible un-matching between the two groups, by adjusting for the confounding factors. Logistic regression analysis will be performed by including all the variables and then retaining those having a statistical significance of $p < 0.1$.

The same statistical analyses will be carried out on the per protocol population; that is, those patients that are randomized and assessed for type of treatment actually administered.

Sample size was calculated on the basis of an expected incidence of TVE equal to ~ 20% of non-treated patients, and ~ 10% of enoxaparin treated patients. Both groups will need approximately 203 patients each, in order to evidence a statistical difference of 50% with an alpha-value equal to 0.05 and a beta value of 0.20. The study will be multi-centered with an expected 20 Italian centers participating over a 2-year enrollment period.

Treatment of data

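### Does the primary endpoint lack a usable time window because symptomatic VTE has no closing day and the ultrasound is placed at the end of follow-up?

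*Combined protocol and SAP*

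**What the plan says.** **Primary endpoint (End-points).** The first component is "symptomatic venous thromboembolism objectively documented as proximal/distal DVT or pulmonary embolism", with no day attached. The second is asymptomatic proximal or distal DVT "documented by ultrasound at the end of follow-up". The Objectives name the same components, also without a time point.

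**Leg ultrasound (Study design and interventions).** The one routine examination "will be performed bilaterally on the lower limbs 10 ± 2 days following the start of treatment". A patient whose symptom-driven scan is negative is scanned again on that same timetable, so no later routine scan is added.

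**Follow-up (same section).** "Follow-ups at 30 and 90 days after cerebral hemorrhage will be performed either in-clinic or over the phone", and their purpose is "in order to monitor for any clinical signs of venous thromboembolism or re-bleeding". "The final follow-up, at 90 days, will be carried out over the phone", by a blinded physician. After the treatment period, therapy is left to the treating physician.

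**Secondary endpoints.** These are intracranial bleeding, extracranial bleeding, disability or death at 90 days, and "Mortality alone at 90 days". None is a VTE endpoint.

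**Day 0.** Patients are randomised 72 hours after onset, and enoxaparin also starts after 72 hours. The control group receives standard therapy alone, with no start date given. The follow-up brain CT uses the same clock: "Brain CT scan will be performed 10 ± 2 days from the start of treatment".

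**Sample size (Statistical analysis).** About 20% of untreated and 10% of enoxaparin patients are expected to have VTE, with alpha 0.05, beta 0.20 and about 203 per group. No time horizon is attached to the rates.

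**The concern.** Three things look wrong together.

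1. Symptomatic VTE has no closing day. A confirmed event on day 40 could be counted by an analyst who runs the endpoint to day 90 and left out by one who stops at the end of treatment.
2. The ultrasound is placed at the end of follow-up, yet follow-up ends with a telephone call. Taken literally, that scan is never scheduled.
3. The scan is dated from the start of treatment, which is undefined for controls. If standard therapy began before randomisation and were used as the start in that group alone, the assessment day could differ by arm.

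The treatment is open, so an unsettled primary window is a fair thing to worry about. Blinded adjudication decides whether an event is VTE, not whether its date qualifies. And if the 20% and 10% were meant for the treatment period only, 203 per group might have been sized for a different endpoint from the one analysed.

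**Working it through.** **Step 1: the window, from the text.** Two readings are possible.

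| Reading | Fits | Does not fit |
|---|---|---|
| Symptomatic VTE counts to day 90; asymptomatic DVT from the scheduled scan | No limit written on symptomatic VTE; 30- and 90-day contacts look for VTE; no other endpoint could use those findings | The words placing the ultrasound at the end of follow-up |
| All VTE closes at the end of treatment | Ultrasound near the end of treatment | The VTE checks at days 30 and 90 would feed no endpoint; a limit must be added that nobody wrote; the plan calls day 90 the final follow-up |

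The first reading needs one phrase to be taken loosely. The second adds a restriction and leaves planned data without a use. The physician's freedom to choose therapy after the treatment period concerns treatment; it does not limit what is counted under intention to treat.

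The missing day also fits a pattern. Disability and mortality, which are measured at a point in time, carry 90 days. Both bleeding endpoints, which are event counts like the primary, carry no day.

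**Step 2: the scan wording.** Only one routine ultrasound exists, so asymptomatic DVT can be counted only from it. The loose phrase does not alter the count.

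**Step 3: day 0.** Both groups are randomised at 72 hours to their assigned therapy, and standard therapy is given in both. Dating from randomisation puts the scan at 10 − 2 = 8 to 10 + 2 = 12 days in each arm. An arm difference arises only if the start is read differently for the two groups.

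**Step 4: the stated sample size.** Pooled-variance normal formula, two-sided alpha 0.05 (sidedness is not stated; two-sided reproduces the figure), 80% power, mean rate p̄ = 0.15:

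n = [1.960·√(2·0.15·0.85) + 0.842·√(0.20·0.80 + 0.10·0.90)]² / 0.10² = (0.9897 + 0.4208)² / 0.01 ≈ 199 per group.

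The stated 203 agrees. Exact power of the uncorrected chi-square test at 203 per group is 0.812.

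**Step 5: how much the window could matter for power.** The documents give no rate of late VTE, so the following are assumptions. They apply only if 20% and 10% cover the treatment period and the primary runs to day 90.

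| Assumed late events | Rates | Power at 203 | n per group for 80% |
|---|---|---|---|
| (a) 1, 3, 5 points added to both arms | 21/11, 23/13, 25/15% | 0.790, 0.751, 0.718 | 210, 231, 250 |
| (b) 1, 3, 5% of event-free patients in each arm | 20.8/10.9, 22.4/12.7, 24.0/14.5% | 0.785, 0.733, 0.685 | 213, 241, 270 |
| (c) 1, 3, 5 points in controls, half that on enoxaparin | 21/10.5, 23/11.5, 25/12.5% | 0.834, 0.872, 0.904 | 188, 169, 152 |

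In (b), the control rate is 0.20 + 0.80L and the enoxaparin rate 0.10 + 0.90L, where L is the late proportion. In (a), 1 to 5 points is 203 × 0.01 ≈ 2 to 203 × 0.05 ≈ 10 events per group. If the design rates already run to day 90, power stays at 0.812.

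**The case for a change.** The strongest case for acting is that neither reading makes every sentence agree. If follow-up means day 90, the endpoint asks for an ultrasound nobody will perform; if it means the end of treatment, the later VTE checks serve no endpoint. A primary window in an open trial should be fixed before outcomes are seen, and the repair would cost only wording.

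Part of this stands. The closing day is not written down, day 90 is an inference, and the ultrasound phrase is inaccurate. A sponsor who later closed the endpoint at the end of treatment could point to no sentence that forbids it outright.

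The rest does not carry. The two readings are not evenly balanced: one tolerates a slip that leaves the count unchanged, while the other imports a limit and discards planned observations. The contrast with the endpoints dated at 90 days loses force once the undated bleeding endpoints are set beside it. The power argument works in both directions and depends on an assumption the plan does not make. The Risk-benefit evaluation also quotes a thromboembolic risk of about 20%, with no restriction to the treatment period. As for the control group's clock, no arm difference is shown, only one that could follow from an unlikely reading. The brain CT shares that clock, but its result bears on suspending heparin, and no view on its timing is offered here.

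**Conclusion.** The observations are accurate, but they do not call for a change. Followed in its natural reading, the plan gives a sound primary result: confirmed symptomatic VTE through the 90-day follow-up, plus asymptomatic DVT at the scheduled scan, in both groups and for all randomised patients. The ultrasound phrase is a clerical slip without effect on the count. The unstated closing day and the control group's day 0 are details that analysts can fill sensibly.

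No stated figure is shown to be wrong. The 203 per group reproduces, with power of about 81%. Under assumed late-event models power ranges from about 69% to 90%, and the number needed from about 152 to 270 per group, on both sides of 203. These ranges are illustrations, not limits.

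The conclusion rests on two inferences: that the 30- and 90-day VTE checks feed the primary endpoint, and that randomisation is day 0 in both arms. Both are the readings the text best supports, though neither is stated.

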COVER LETTER

1st June, 2011

PREVENTIHS STUDY
PREvention of VENous Thromboembolism In Hemorrhagic Stroke patients

NCT01573169

PREVENTIHS STUDY

PREvention of VENous Thromboembolism In Hemorrhagic Stroke patients

Introduction

Venous thromboembolism (VTE) is a common life-threatening complication in patients with stroke. In these patients, an average incidence of asymptomatic deep-vein thrombosis (DVT) of 50% has been reported (1). Additionally, pulmonary embolism (PE) has been reported to occur in 2% of patients with stroke (2) and 5% of early deaths after stroke is reported to be due to PE (3). Prospective trials have shown that both unfractionated heparin and low molecular weight heparin are effective in reducing VTE and PE in ischemic stroke patients (4). Current guidelines recommend the use of these agents in ischemic stroke patients with risk factors for VTE (5). The role of anticoagulants for the prevention of VTE in acute hemorrhagic stroke is uncertain and anticoagulant agents have not gained wide acceptance because of concern about possible increases in hematoma enlargement. To support this, a recent meta-analysis has indicated that in patients with hemorrhagic stroke, early anticoagulation is associated with a significant reduction in PE and a non-significant reduction in mortality, with the trade-off of a non-significant increase in hematoma enlargement (6). These meta-analysis results cannot be reliably applied to clinical practice due to the low quality of the studies included.

Objectives

In this multicenter, randomized trial, the use of standard treatment alone (compression stockings and /or intermittent pneumatic compression and /or early mobilization) will be compared with the use of standard treatment plus the

administration of the low molecular weight heparin enoxaparin for the prevention of VTE in patients with acute hemorrhagic stroke. Enoxaparin will be started after 72 hours from stroke onset and will be continued for 10 days. The principal outcome measures will be symptomatic, objectively confirmed VTE or asymptomatic DVT (proximal and/or distal) as assessed by ultrasound examination. Because the use of anticoagulants in patients with hemorrhagic stroke could be associated with a high risk of re-bleeding, the safety of enoxaparin in this clinical setting will also be assessed.

Methods

Study population

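### Secondary end-point 2 sorts non-major extracranial bleeds partly by interruption of study treatment, a criterion wider in the enoxaparin arm, so the same bleed can be classed differently by arm

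*Combined protocol and SAP*

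**What the plan says.** All in the combined protocol and SAP.

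- End-points, secondary end-point 2, opens with two classes: "The number of extracranial bleedings will be divided into two groups: major and minor". After defining major bleeding, it says that medical intervention for an event that misses those criteria, "including any interruption of study treatment, will be considered clinically relevant but not a major bleeding". It closes with "All other bleedings will be considered minor". The definitions therefore produce three classes.
- Study design and interventions: patients are randomised "to receive enoxaparin 0.4 ml die plus standard therapy (group A) or standard therapy alone (group B"). Objectives lists standard treatment as "compression stockings and /or intermittent pneumatic compression and /or early mobilization". There is no placebo.
- Study population describes a "multicentre, prospective, randomised, open, blinded endpoint clinical trial". Under Study design and interventions, "intra- and extra-cranial hemorrhagic events will be judged blindly on the type of treatment received".
- Statistical analysis: primary and secondary endpoints are compared between arms by chi-square, without adjustment.

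**The concern.** A safety class should depend on the bleed, or at least on responses that are equally possible in both arms. Here one entry route to the middle class is an action on the randomised treatment. Group A has a drug that can be held, and group B does not. A minor nosebleed after which enoxaparin is held for a day moves up a class in group A; in group B the same nosebleed has no drug to hold and stays minor.

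The move empties one class and fills the other, in one arm. With identical bleeding, enoxaparin can appear to cause fewer minor and more clinically relevant bleeds. Objectives makes the safety of enoxaparin a stated aim, so a reader of the results would be likely to interpret both differences.

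**Working it through.** **Step 1: how a non-major bleed is classed, by arm.**

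| Consequence of the bleed | Group A | Group B |
|---|---|---|
| Medical intervention other than interruption | clinically relevant | clinically relevant |
| Stockings or compression interrupted | clinically relevant, if these count as study treatment | same |
| Enoxaparin interrupted, nothing else | clinically relevant | cannot occur; the same bleed is minor |
| None | minor | minor |

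Only the third row differs by arm. The criterion is wider in group A, not exclusive to it. The total of non-major bleeds is the same under either classification.

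**Step 2: the plan's own figure.** The only computed design figure is 203 per group, for 20% versus 10% on the primary endpoint, alpha 0.05, beta 0.20. Two-sided, without continuity correction:

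n = [1.96 × √(2 × 0.15 × 0.85) + 0.842 × √(0.20 × 0.80 + 0.10 × 0.90)]² / 0.10² = 199.

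This is within 3% of 203. The point does not depend on it; 203 is used below only as the arm size.

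**Step 3: illustration.** The documents give no rate of extracranial bleeding and none of interruption, so these inputs are assumptions:

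- T: true non-major bleeding, equal in both arms: 2%, 6% or 10%.
- g = 20%: share of bleeds with another intervention, equal in both arms.
- f: share of the remaining bleeds in group A whose only consequence is holding the drug: 25% or 50%.

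Clinically relevant: A = T × [g + (1 − g) × f]; B = T × g. Minor: A = T × (1 − g) × (1 − f); B = T × (1 − g).

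For T = 10%, f = 50%: clinically relevant is 10% × (0.2 + 0.8 × 0.5) = 6% in A against 2% in B, or 12.2 against 4.1 expected patients. Minor is 4% against 8%, or 8.1 against 16.2.

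The chance of a significant result was found by exact enumeration of two binomials, 203 per arm, with the uncorrected two-sided chi-square test at 0.05:

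| T | f | Clinically relevant, A vs B | Falsely significant | Minor, A vs B | Falsely significant |
|---|---|---|---|---|---|
| 10% | 25% | 4.0% vs 2.0% | 21% | 6.0% vs 8.0% | 12% |
| 10% | 50% | 6.0% vs 2.0% | 56% | 4.0% vs 8.0% | 39% |
| 6% | 25% | 2.4% vs 1.2% | 13% | 3.6% vs 4.8% | 9% |
| 6% | 50% | 3.6% vs 1.2% | 34% | 2.4% vs 4.8% | 25% |
| 2% | 25% | 0.8% vs 0.4% | 4% | 1.2% vs 1.6% | 6% |
| 2% | 50% | 1.2% vs 0.4% | 11% | 0.8% vs 1.6% | 10% |

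With all non-major bleeds compared together, the same enumeration gives 4.5%, 4.7% and 4.8% at T = 2%, 6% and 10%. With f = 0 and T = 10% it gives 4.5% for the clinically relevant class.

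**The case against.** **The biased comparison may not be planned.** Two groups are announced, and no test of the middle class is specifically listed. If every non-major bleed were counted as minor, the bias would vanish. This stands as an ambiguity. But the closing sentence makes minor the remainder after the middle class is removed, so the rule followed as written gives the biased split.

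**Adjudication is blind.** True, but the classifying fact is an action already taken by a clinician who knows the arm. Documentation that enoxaparin was stopped also reveals the arm to the committee.

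**Interruption is not confined to group A.** A reader might infer that group B can never meet the criterion. The documents do not support that: the text says study treatment, not study drug, and Risks of treatments and procedures mentions "complications such as ulcers and subcutaneous hematomas due to the use of elastic stockings". Stockings or compression could be interrupted, but in either arm, so the drug remains an additional route in A.

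**The size could be overstated.** A reader might model the middle class as empty in group B. At 10% bleeding, with a quarter to a half of A's bleeds reclassified, that gives false significance in 75%-99% of trials for the class. The definition does not support it, because interruption is one form of medical intervention and other forms count in both arms.

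**Stopping a drug is a real consequence.** It is, and it deserves reporting. It does not make a fair between-arm outcome when one arm has no drug to stop.

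**Conclusion.** The point holds for the split of non-major extracranial bleeds: fewer minor and more clinically relevant in group A when true bleeding is equal. It applies only to bleeds whose sole consequence is stopping enoxaparin, so the same bleed can be, not always is, classed differently.

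The size cannot be fixed from the documents. Under the stated assumptions, false significance for the clinically relevant class is 21%-56% at 10% bleeding, 13%-34% at 6% and 4%-11% at 2%. For minor bleeding it is 12%-39%, 9%-25% and 6%-10%. The effect becomes negligible as bleeds or interruptions become few; at 2% bleeding with a quarter reclassified there is no real inflation.

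A reader might infer that the safety assessment as a whole is compromised. It is not: major bleeding, total extracranial bleeding, intracranial bleeding, mortality and the primary endpoint do not use this criterion. The mismatch between two announced and three defined classes needs no assumption and must be resolved in any case.

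**What to change.** In secondary end-point 2:

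1. Make the between-arm comparisons major extracranial bleeding and all non-major extracranial bleeding.
2. If a clinically relevant subclass is kept, define it only by interventions that either arm can have, and leave interruption of study treatment out of the definition.
3. Report bleeding-related interruption of study treatment descriptively.
4. Make the announced number of classes agree with the classes used.

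The cost is a few words in one endpoint definition and a smaller clinically relevant class. No extra data are needed, and the sample size stays at 203 per group. Even when redefined, the subclass would rest on decisions by unblinded clinicians, so all non-major bleeding should carry the comparison. The change concerns how events are classified, not when treatment is stopped.

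### The only adjusted analysis depends on an undefined imbalance, an unlisted variable pool and pruning at p < 0.1; one pre-specified supportive logistic model should replace it, with the unadjusted results still governing

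*Combined protocol and SAP*

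**What the plan says.** All of the relevant text is in the Statistical analysis section, apart from the baseline measurements noted last.

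- **Governing analysis.** The groups are compared by chi-square, with odds ratio (OR), relative risk (RR) and confidence intervals, by intention to treat. The plan states: "All predefined endpoints will be assessed without adjusting for confounding factors".
- **Trigger for adjustment.** A logistic regression, labelled post-hoc, is to be run "in the face off any possible un-matching between the two groups". No variable, measure or threshold defines this.
- **Selection.** "Logistic regression analysis will be performed by including all the variables and then retaining those having a statistical significance of" p < 0.1. No list of variables is given. The text does not say that treatment is kept regardless of its p-value.
- **Second population.** The same analyses are repeated on what the plan calls the per protocol population, described as "those patients that are randomized and assessed for type of treatment actually administered".
- **Planning rates.** The sample size uses an "expected incidence of TVE equal to ~ 20% of non-treated patients, and ~ 10% of enoxaparin treated patients", with 203 patients per group.

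No other section names a covariate or a stratification factor. On baseline measurements, Study population uses "a score of 3 or 4 per item 6 of the NIHSS" for eligibility. Study design and interventions has "a brain CT scan which will be considered the baseline examination" before randomisation, and its rule for clinical worsening, "defined as an increase of 4 points or more on the NIHSS score", implies an earlier total score without saying when it is recorded.

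**The concern.** If the randomisation is sound, baseline differences between the randomised groups arise by chance. A trigger based on such differences lets chance decide whether an adjusted estimate is produced at all. The trigger is also undefined, so two analysts could decide differently on the same data.

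Once triggered, the model starts from an open-ended set of variables on few events and keeps whichever pass p < 0.1. The covariate set, and hence the treatment estimate, then partly reflects selection. As written, the retention rule also applies to treatment, so the model could end without the effect that it is meant to estimate.

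In the population grouped by treatment actually administered, differences between groups are not only chance. The plan does not warn that the same regression cannot be relied on to remove that confounding.

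At stake is the credibility and reproducibility of a supportive estimate. The primary test is not at stake.

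**Working it through.** **1. The plan's own figure.** Inputs from Statistical analysis: 20% versus 10%, alpha 0.05 (two-sided assumed), power 0.80.

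n per group = [1.96·√(2·0.15·0.85) + 0.8416·√(0.20·0.80 + 0.10·0.90)]² / 0.10² = (0.990 + 0.421)² / 0.01 ≈ 199.

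The plan states 203, so the figure reproduces. Power at 203 per group is 80.8%.

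**2. Events per model term.** Expected primary events = 203 × 0.20 + 203 × 0.10 = 60.9. The counts of 8 and 20 candidates are assumptions, because the plan gives none.

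| Model | Terms (treatment + covariates) | Events per term |
|---|---|---|
| Fixed, 3 covariates | 4 | 60.9/4 = 15.2 |
| Start from 8 candidates | 9 | 60.9/9 = 6.8 |
| Start from 20 candidates | 21 | 60.9/21 = 2.9 |

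**3. How often chance would fire the trigger.** Assume, since the plan is silent, that un-matching means at least one independent baseline variable with p < 0.05. The probability is 1 − 0.95^k: 34% for k = 8 and 64% for k = 20.

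**4. Noise variables kept.** If 3 of the candidates are prognostic, the chance of keeping at least one of the others at p < 0.1 is about 1 − 0.9^5 = 41% (8 candidates) or 1 − 0.9^17 = 83% (20). Simulation gave 41-43% and 84-86%.

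**5. Fixed against pruned model.** Simulated trials had 203 per arm, rates of 20% versus 10%, treatment forced in, and three prognostic covariates with an assumed OR per SD between 1.0 and 2.0. Pruning means: fit all candidates, keep p < 0.1, refit. The first row spans several separate sets of runs; the others come from one set of 3,000 runs per cell.

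| Result | 8 candidates | 20 candidates |
|---|---|---|
| Treatment OR differs by > 5% | 8-13% | 24-38% |
| Treatment OR differs by > 10% | 1-3% | 8-16% |
| Disagreement on p < 0.05 | 1.1-2.2% | 2.8-3.5% |

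- **Coverage of the 95% interval:** 94.7-95.7% fixed; 94.0-95.1% pruned from 20.
- **Mean OR at covariate OR 1.6** (true conditional OR 0.415): 0.402 fixed; 0.392 pruned from 20.
- **With 10 candidates** (three with log-OR 0.5 per SD; 4,000 runs): type I error 5.3% fixed and 5.4% pruned; power 84% for both.

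**6. The rule applied literally to treatment.** With no effect, p ≥ 0.1 occurs in about 90% of trials by definition. At the planned effect, use the unadjusted approximation:

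- null SE = √(2·0.15·0.85/203) = 0.0354; alternative SE = √(0.25/203) = 0.0351
- P(p < 0.1) ≈ Φ[(0.10 − 1.645 × 0.0354)/0.0351] = Φ(1.19) = 0.88

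Treatment would therefore be dropped in about 12% of trials. Simulation gave 89-91% with no effect and 9-12% at the planned effect.

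**7. Cost of a fixed model when its covariates are not prognostic.** Power for VTE goes from 80.5% (unadjusted) to 80.3% (fixed). Other runs also showed a loss of under 1 point.

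**The case against.** The strongest reply is that nothing that governs depends on this regression. The plan makes the unadjusted results the predefined analysis and labels the regression post-hoc. With treatment kept in, the pruned model performs almost as well as the fixed one. This stands, and it limits the weight of the point.

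The larger percentages rest on assumptions. The plan states neither 8 nor 20 candidates, nor a p < 0.05 trigger. The measure of difference also takes the fixed model as yardstick: even where no covariate matters, 28% of trials differ by more than 5% with 20 candidates. The phrase about all variables could also mean only the confounding factors just mentioned. These replies stand as to size. They do not supply the missing list, threshold or statement about treatment.

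The covariates suggested below are not derived from the documents, which do not link age, NIHSS or haematoma volume to VTE. Centre and anticoagulant-related haemorrhage could also be proposed. This stands, so the set is for the sponsor to confirm.

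A reader might infer that a fixed model removes the false-positive risk of choosing the better of two results. It does not. With no effect and covariate OR 1.6, either result was significant in 6.8% of simulated trials for chi-square or the fixed model, against 7.1% for chi-square or the model pruned from 20. Most of the excess comes from having two estimates, so it is no argument for the change.

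**Conclusion.** The point holds as a modest defect in a supportive analysis. Chance decides whether the adjusted estimate exists and which covariates it contains, and the literal rule can remove treatment. That much follows from the text and the roughly 61 expected events. How far the estimate moves depends on the assumed candidate count: differences above 5% in about 8-13% of trials with 8 candidates and 24-38% with 20. Changes in significance are rare, at most 3.5% in those runs.

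A reader might infer that the p < 0.1 rule undermines the trial's conclusion or materially inflates type I error. The documents do not support that, because the unadjusted chi-square, OR and RR are valid and govern. Nor is power a reason for the change: any gain would depend on assumed prognostic strength and would fall in a non-governing analysis. Dropping treatment is what the literal wording permits; the plan does not state it as an intention.

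**What to change.** In Statistical analysis:

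- **Delete** the imbalance trigger and the p < 0.1 rule.
- **Pre-specify one supportive logistic model.** Treatment is always retained, with a short fixed list of baseline covariates settled before anyone sees outcomes by arm. Suitable candidates, for the sponsor to confirm, are age, total NIHSS at randomisation and log haematoma volume on the baseline CT. State that the total NIHSS is recorded at randomisation.
- **Missing baseline values:** fill with the mean pooled over both arms, so that all randomised patients stay in.
- **Reporting:** name the endpoints that the model covers and show it beside the unadjusted results, which govern for every endpoint. Label any other adjusted model exploratory.
- **As-treated population:** state that the model does not remove confounding there.

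The cost is SAP wording, one regression per covered endpoint and the explicit NIHSS recording. Sample size, primary test and patient management do not change. The adjusted OR is conditional on the covariates, so it is not directly comparable with the unadjusted OR, and the report should say so. Power in the supportive model falls by under 1 point if the covariates are not prognostic. Choosing the wrong form for volume (log or linear) cost at most 1.5 points of power for VTE in simulation. The documents give no expected event counts for the secondary endpoints, so the sponsor should check that the model is not too large for them.
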